6 Urinalysis: leukocytes, nitrite, protein, glucose, ketones, blood, pH, urobilinogen, bilirubin, hemoglobin – dipstick.

7 V1a: Height has to be determined for all subjects. V1b to V6: Height has only to be determined in adolescent subjects (i.e. < 18 years of age).

8 In addition, each subject will perform a urine dipstick pregnancy test at home at the beginning of each new medication cycle. In case of an equivocal or positive urine pregnancy test, a quantitative serum pregnancy test has to be performed for confirmation.

9 On Day 10 + 2 days of each cycle, the subjects will be called by the site staff to collect information on adverse events which might have occurred, and to confirm e-diary compliance. Throughout each cycle, subjects will be called by site staff to review e-diary compliance as needed.

10 Only electrolytes.

11 Measurements of vital signs will be repeated twice with a break of one minute between them at each visit in sitting position, after at least five minutes of rest. The subject should not talk.

12 Two blood samples per visit will be collected to determine plasma concentrations of LF111 at Visits 2 and 4 and should ideally be one hour apart (between 45 and 120 minutes after the first sample) without a LF111 administration in between.

13 The subject will be asked if she has a wish of pregnancy at each visit. In case of a positive answer, the subject will be discontinued.

14 Once the e-diary has been assigned to a subject, a practice diary (training section in e-diary) has to be actively completed.

15 The investigator should arrange for the subject's further contraceptive treatment or make an appropriate referral, as needed, at V5. Consecutive contraceptives should be started after last IMP intake and should be used at least until V7/Follow-up. This arrangement is outside the trial and costs will not be covered by the Sponsor.

16 The subject will be asked by the investigator: Are you satisfied with this method? Answer options: strongly agree, agree, undecided, disagree, strongly disagree, no answer. Furthermore, for women who switched from another oral contraceptive method to the IMP will be asked by the investigator: How was your wellbeing during the intake of the IMP in comparison to the time when you took your former oral contraceptive? Answer options: better, unchanged, worse, no answer.

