All analyses described above in women aged ≤ 35 years (at the time of trial enrollment) will also be evaluated for the whole subject population. Included are only cycles of non-breastfeeding women with sexual activity without using back-up contraception.

- Overall PI, PI for method failures, PI for evaluable cycles and pregnancy ratio (life table analysis) in women aged > 35 years

All analyses described above in women aged ≤ 35 years (at the time of trial enrollment) will also be evaluated for women aged > 35 years at study enrollment. Included are only evaluable cycles of non-breastfeeding women with sexual activity without using back-up contraception.

Overall PI will be based on exposure cycles.

Efficacy Endpoints in Addition to the Protocol

- Overall PI based on only confirmed and on confirmed and suspected, non-confirmed pregnancies (with and without sites 104 and 120)

Overall PI based on exposure cycles will be evaluated for the whole subject population. Included are only cycles of non-breastfeeding women. The overall PI will be evaluated based on only confirmed pregnancies and on confirmed and suspected, non-confirmed pregnancies and in- and excluding sites 104 and 120.

All analyses described above will be evaluated in addition by BMI subgroup and by weight subgroup.

- PI for evaluable cycles in women aged ≤ 35 years in total and by BMI and weight groups (with and without sites 104 and 120) based on confirmed and on confirmed and suspected, non-confirmed pregnancies

PI based on evaluable cycles will be evaluated in women aged ≤ 35 years. Included are only cycles of non-breastfeeding women. The PI will be evaluated based on only confirmed pregnancies and on confirmed and suspected, non-confirmed pregnancies and in- and excluding sites 104 and 120.

All analyses described above will be evaluated in addition by BMI subgroup and by weight subgroup.

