5.5 Efficacy Analysis

Primary and secondary efficacy analysis will be based on calculations of the PI in several different cases for non-breastfeeding women. The general formula of PI is

$$PI(<\text{set of cycles}>) = \frac{\sum \text{on-drug pregnancy} \in \{<\text{set of cycles}>\}}{\#\{<\text{set of cycles}>\}} \times 1300.$$

A two-sided 95% CI for the PI will be calculated assuming that events of pregnancy have a Poisson distribution. The CI will be calculated using the following equations from Gerlinger et al. [4]:

$$CI_{lower}(PI(<\text{set of cycles}>)) = \frac{1300}{\#\{<\text{set of cycles}>\}} \times CI_{lower}(\#\{\text{pregnancy} \in \{<\text{set of cycles}>\}\}),$$

$$CI_{upper}(PI(< set of cycles >)) \\ = \frac{1300}{\#\{< set of cycles >\}} \times CI_{upper}(\#\{pregnancy \in \{< set of cycles >\}\}),$$

where

$$CI_{lower}(\#\{pregnancy \in \{< set of cycles >\}\}) \\ = 0.5\chi^2(0.025; 2 \times \#\{pregnancy \in \{< set of cycles >\}\}),$$

$$CI_{upper}(\#\{pregnancy \in \{< set of cycles >\}\}) \\ = 0.5\chi^2(0.025; 2 \times \#\{pregnancy \in \{< set of cycles >\}\} + 1),$$

where $\chi^2(\alpha; n) = \alpha$ -Quantile of χ^2 -distribution with parameter n .

The following information from Pregnancy Notification forms will be taken:

- Subject ID number
- Estimated date of conception
- Method(s) Used to Estimate Conception Date

Efficacy analysis definitions

Term	Definition
Confirmed pregnancy	Subject reported a positive urine home pregnancy test and the pregnancy was confirmed by qualitative urine pregnancy test (β -hCG) and quantitative serum pregnancy test (β -hCG).
Suspected, non-confirmed pregnancy	Subject reported a positive urine home pregnancy test but confirmatory qualitative urine pregnancy test (β -hCG) and/or quantitative serum pregnancy test (β -hCG) are missing.
Suspected, subject confirmed not pregnant	Subject reported a positive urine home pregnancy test but confirmatory qualitative urine pregnancy test (β -hCG) and/or quantitative serum pregnancy test (β -hCG) are negative.
On-drug pregnancy	An on-drug pregnancy includes all conceptions that occur from Day 1 (the initiation of study medication) through seven days after the final tablet (active or placebo) is taken.

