5.5.1 Primary Efficacy Analysis

Analysis of the primary efficacy variable defined as PI based on evaluable cycles in non-breastfeeding women aged ≤ 35 years will be performed for the MFAS.

$$PI \text{ (evaluable cycles)} = \frac{\sum \text{on-drug pregnancy} \in \{\text{evaluable cycles}\}}{\#\{\text{evaluable cycles}\}} \times 1300.$$

Respective two-sided 95% CI for PI based on evaluable cycles will be calculated according to formula in Section 5.5.

Tables

No.	Name	Analysis set	Comments
Table 15.2.1.1.1	Pearl Index Based on Evaluable Cycles in Non-Breastfeeding Women Aged ≤ 35 Years (Only Confirmed Pregnancies, Excluding Sites 104 and 120)	Modified Full analysis	Number and percentage of confirmed on-drug pregnancies in the evaluable cycles will be presented. Number of evaluable cycles as well as PI and two-sided 95% CI will be presented. Table analysis will be based on MFAS. Data of centers 104 and 120 will be excluded.

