Table 15.2.1.4.3 _add	Pearl Index Based on Evaluable Cycles in Non-Breastfeeding Women Aged \leq 35 Years (Only Confirmed Pregnancies, Including Sites 104 and 120)	Modified Full analysis	Number and percentage of confirmed on-drug pregnancies in the evaluable cycles will be presented. Number of evaluable cycles as well as PI and two-sided 95% CI will be presented. Table analysis will be based on MFAS. Data of centers 104 and 120 will be included.

Table 15.2.1.4.4 _add	Pearl Index Based on Evaluable Cycles in Non-Breastfeeding Women Aged ≤ 35 Years (Confirmed and Suspected, Non-confirmed Pregnancies, Excluding Sites 104 and 120)	Modified Full analysis	Number and percentage of confirmed and suspected, non-confirmed on-drug pregnancies in the evaluable cycles will be presented. Number of evaluable cycles as well as PI and two-sided 95% CI will be presented. Table analysis will be based on MFAS. Data of centers 104 and 120 will be excluded.
Table 15.2.1.4.5 _add	Pearl Index Based on Evaluable Cycles in Non-Breastfeeding Women Aged ≤ 35 Years (Confirmed and Suspected, Non-confirmed Pregnancies, Including Sites 104 and 120)	Modified Full analysis	Number and percentage of confirmed and suspected, non-confirmed on-drug pregnancies in the evaluable cycles will be presented. Number of evaluable cycles as well as PI and two-sided 95% CI will be presented. Table analysis will be based on MFAS. Data of centers 104 and 120 will be included.
Table 15.2.1.4.6 _add	Pearl Index Based on Evaluable Cycles in Non-Breastfeeding Women Aged ≤ 35 Years by BMI Subgroup (Only Confirmed Pregnancies, Excluding Sites 104 and 120)	Modified Full analysis	Number and percentage of confirmed on-drug pregnancies in the evaluable cycles will be presented. Number of evaluable cycles as well as PI and two-sided 95% CI will be presented by BMI subgroup. Table analysis will be based on MFAS. Data of centers 104 and 120 will be excluded.
Table 15.2.1.4.7 _add	Pearl Index Based on Evaluable Cycles in Non-Breastfeeding Women Aged ≤ 35 Years by BMI Subgroup (Only Confirmed Pregnancies, Including Sites 104 and 120)	Modified Full analysis	Number and percentage confirmed of on-drug pregnancies in the evaluable cycles will be presented. Number of evaluable cycles as well as PI and two-sided 95% CI will be presented by BMI subgroup. Table analysis will be based on MFAS. Data of centers 104 and 120 will be included.

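### Two pregnancy categories in SAP Section 5.5 overlap, and one takes in a serum-positive woman, so the numerator of the wider Pearl Index tables is partly wrong and partly undetermined

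*SAP*

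**What the plan says.** The definitions table in SAP Section 5.5 has three rows for a woman who reports a positive home test.

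- *Confirmed pregnancy*: "Subject reported a positive urine home pregnancy test and the pregnancy was confirmed by qualitative urine pregnancy test" and also by the quantitative serum test. Both must be positive.
- *Suspected, non-confirmed*: the confirmatory urine test "and/or quantitative serum pregnancy test (β -hCG) are missing".
- *Suspected, subject confirmed not pregnant* (below, 'confirmed not pregnant'): the confirmatory urine test "and/or quantitative serum pregnancy test (β -hCG) are negative".

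None of the three rows says which test prevails when the two disagree, or how soon after the home test they must be done. Footnote 8 to the schedule in SAP Section 1 says that after an equivocal or positive urine test "a quantitative serum pregnancy test has to be performed for confirmation".

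The primary table (15.2.1.1.1, Section 5.5.1) counts confirmed pregnancies only: "Number and percentage of confirmed on-drug pregnancies in the evaluable cycles will be presented". For the additional efficacy endpoints, Section 2.2.2 states: "The PI will be evaluated based on only confirmed pregnancies and on confirmed and suspected, non-confirmed pregnancies". Table 15.2.1.4.4 is one of the wider tables: "Number and percentage of confirmed and suspected, non-confirmed on-drug pregnancies in the evaluable cycles will be presented". No Pearl Index table counts the third category. Section 3.3 leaves it to the data review meeting to assign each pregnancy to a category and gives no rule for discordant or late tests.

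**The concern.** The wider tables show how far the Pearl Index depends on requiring full confirmation. For that, every positive home test must fall into exactly one category, and the category must agree with the test that the plan itself treats as confirming. The rows fall short in three ways.

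1. Because of the 'and/or', one negative result is enough for 'confirmed not pregnant'. A woman with a negative confirmatory urine test and a positive serum test is therefore labelled not pregnant against the trial's own confirming test.
2. The 'missing' row and the 'negative' row can both be true of the same woman. She is counted under one and not under the other.
3. On-drug pregnancy is defined by conception. With no interval stated, a negative test taken after an early loss satisfies the 'confirmed not pregnant' row just as a prompt one does.

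At stake is the reliability of a sensitivity analysis. A reader comparing the wider tables with the primary table could not tell whether a small difference reflects few doubtful cases or the way such cases were sorted.

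**Working it through.** **Classification.** Inputs are the three rows of Section 5.5, applied literally to each urine/serum combination after a positive home test.

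| Urine | Serum | Category as written | In wider tables? |
|---|---|---|---|
| + | + | confirmed | yes |
| + | − | confirmed not pregnant | no |
| + | missing | suspected, non-confirmed | yes |
| − | + | confirmed not pregnant | no |
| − | − | confirmed not pregnant | no |
| − | missing | both rows | undetermined |
| missing | + | suspected, non-confirmed | yes |
| missing | − | both rows | undetermined |
| missing | missing | suspected, non-confirmed | yes |

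Of the eight patterns that are not confirmed, one is serum-positive yet classed as not pregnant, and two sit in both rows. Giving either row precedence would settle the two overlaps. It would not help urine-negative/serum-positive, where nothing is missing. A loss before testing would appear as −/− and be left out.

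**Planned denominator.** Section 2.6 gives 920 subjects, 24.8% using back-up or having no intercourse, 45% dropout and a target of 5000 evaluable cycles; treatment lasts 13 cycles. If dropouts contribute no cycles:

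- cycles per subject = 13 × (1 − 0.248) × (1 − 0.45) = 5.3768
- 920 × 5.3768 = 4947 cycles, and 5000 / 5.3768 = 930 subjects

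This is within about 1% of the plan's figures, so 5000 is a fair working denominator. If dropouts instead left on average halfway through, 920 × 13 × 0.752 × 0.775 = 6970 cycles.

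**Effect per woman.** PI = 1300 × pregnancies / cycles.

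- At 5000 cycles: 1300/5000 = 0.26
- At 6970 cycles: 1300/6970 = 0.19

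**Illustration.** The documents give no pregnancy counts, so those below are assumptions. Limits are exact Poisson at 5000 cycles: lower (1300/5000) × 0.5 × χ²(0.025; 2x), upper (1300/5000) × 0.5 × χ²(0.975; 2x + 2). The standard upper limit is used because the one printed in Section 5.5 (0.025 quantile, 2x + 1 degrees of freedom) gives 1.34 at x = 10, below the estimate of 2.60. That is a separate matter.

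| Counted | As counted | One woman added | Three women added |
|---|---|---|---|
| 5 | 1.30 (0.42–3.03) | 1.56 (0.57–3.40) | 2.08 (0.90–4.10) |
| 10 | 2.60 (1.25–4.78) | 2.86 (1.43–5.12) | 3.38 (1.80–5.78) |
| 20 | 5.20 (3.18–8.03) | 5.46 (3.38–8.35) | 5.98 (3.79–8.97) |

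**The case against.** The strongest reply is that this is a drafting ambiguity in an analysis added to the protocol, and that the data review meeting, which includes a physician, exists to settle such cases and any outstanding SAP issues. Listings 16.2.2.1, 16.2.2.2 and 16.2.5.4 keep pregnancies and test results open to inspection. Much of this stands. The meeting could depart from the wording, so the exact statement is that these women would be left out under the definitions as written. But no rule tells the meeting what to do with discordant tests, and listings do not enter a Pearl Index.

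Four stronger readings are tempting and are not supported.

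- *The rules can only remove pregnancies from the wider tables.* That is true of urine-negative/serum-positive women and of late tests after a loss. It is not true of the two overlapping patterns: under the 'missing' row, a woman with urine missing and serum negative is counted, which raises the index.
- *Serum-positive women in general are dropped.* Serum-positive with urine positive is confirmed, and serum-positive with urine missing is suspected and counted. Only those with a negative confirmatory urine test are affected.
- *A negative test up to 112 days later would be the usual case.* Day 1 of cycle 10 to Day 29 of cycle 13 is 3 × 28 + 28 = 112 days, but only if nothing happens until Visit 6. Footnote 8 does not defer the serum test to a visit, and footnote 9 adds a call at Day 10 (+2) of every cycle. The calls cover adverse events and diary compliance, so they make a long gap less likely without ruling it out.
- *The trial sets no time limit anywhere.* The protocol text available here is the synopsis. The supported statement is that the SAP definitions set none.

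The SAP does not call the wider tables a worst case, and they should not be judged as if it had promised one.

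**Conclusion.** The concern holds for the wider tables. One pattern, urine-negative/serum-positive, is classed against the plan's own confirming test and left out of both Pearl Index versions. Two patterns have no determined category, with an effect in either direction. A conception lost before the confirmatory test could be classed as no pregnancy; how often cannot be told from the documents.

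Each reclassified woman is worth 0.26 on the index at 5000 evaluable cycles (0.19 at 6970), assuming that she belongs to the table's population and that the conception was on-drug. The number of such women is unknown. The documents supplied give no success threshold, so it cannot be said that any conclusion would change, or that the wider tables would give false reassurance. The primary table counts confirmed pregnancies only and is unaffected by these two rows. The rows should still be corrected, because a stated rule that gives a wrong or indeterminate count is more than a missing detail.

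**What to change.** Rewrite the two rows so that they are mutually exclusive.

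- *Confirmed not pregnant*: only when the quantitative serum test is negative and no positive confirmatory test, ultrasound or pregnancy outcome shows a pregnancy.
- *Suspected, non-confirmed*: every other positive home test that is not a confirmed pregnancy, including urine-negative/serum-positive and all serum-missing cases.

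On the table above, this moves +/− and −/+ into the suspected row, settles −/missing as suspected and settles missing/− as not pregnant, absent other evidence. Count the suspected row in Tables 15.2.1.4.4, 15.2.1.4.5, 15.2.3.1.1, 15.2.3.1.3 and their BMI and weight versions.

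Where home-test dates are available, prespecify and justify a maximum interval after the positive home test within which a negative serum test is accepted. The documents imply no particular length and do not say that the date of the first positive home test is recorded, so its availability should be checked first.

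The cost is two definition rows and a rerun of the affected tables. Some false-positive home tests will enter the sensitivity analysis, so its Pearl Index may be slightly less favourable. The primary table does not change.

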1. FLOW CHART AND VISIT SCHEDULE

Table 1: Schedule of Trial Procedures

Visits		V1a (Screening)	V1b (Medication Dispensation)	V2	V3	V4	V5	V6/EDV	V7 (Follow-Up)
Medication cycle	3 to 4 weeks			1	3	6	9 ⁽¹⁵⁾	13 ⁽¹⁾	10 to 14 days after V6⁽²⁾
				Day 20 ± 2 of medication cycle				Day 29 +2	
Informed consent/assent	x								
Demography	x								
Medical and gynecological history ⁽³⁾	x								
Prior medication/contraceptive devices	x								
Concomitant medication/contraceptive devices	x		x	x	x	x	x	x	
Wish of pregnancy ⁽¹³⁾	x	x	x	x	x	x	x	x	
Physical examination	x				x			x	
Vital signs ^(4, 11) , body weight and height ⁽⁷⁾	x	x	x	x	x	x	x	x	
Gynecological examination	x				x			x	
Transvaginal ultrasound	x							x	
Cervical cytology (Pap smear)	x ⁽¹⁹⁾							x ⁽¹⁹⁾	
Routine laboratory parameters ⁽⁵⁾	x		x ⁽¹⁷⁾	x ⁽¹⁰⁾	x	x ⁽¹⁰⁾	x	x	
Pharmacokinetic analysis ⁽¹²⁾			x		x				
Urinalysis ⁽⁶⁾	x				x			x	
Serum pregnancy test	x								
Urine pregnancy test ⁽⁸⁾		x	x	x	x	x	x	x	x
In-/exclusion criteria	x	x							
Dispensing of IMP		x ⁽²⁰⁾	x	x	x	x			
Drug accountability			x ⁽¹⁸⁾	x	x	x	x	x	
IMP acceptability ⁽¹⁶⁾				x				x	
Discuss consecutive contraceptive method						x			
Dispense/collect e-diary		x ⁽¹⁴⁾						x	
Review e-diary ⁽⁹⁾			x	x	x	x	x	x	
Adverse events ⁽⁹⁾	x	x	x	x	x	x	x	x	x

- 1 Assessments are to be performed after completion of cycle 13 and also in case of early discontinuation.
- 2 The post treatment evaluation is to be performed by interviewing the subjects. Inquiries are to be made regarding menstrual cycle, possible return of fertility, and possible use of contraceptive.
- 3 Including check of venous thromboembolism (VTE) risk.

4 Blood pressure and pulse.

5 Laboratory parameters: hematology, biochemistry.

Hematology: hemoglobin, red blood cell count, mean corpuscular volume (MCV) and associated parameters, hematocrit, MCH, white blood cell count, differential white blood cell count including neutrophils, lymphocytes, eosinophils, basophils and monocytes, platelet count.

Biochemistry: sodium, potassium, chloride, creatinine, blood urea nitrogen (BUN), calcium, glucose, total proteins, albumin, total cholesterol (HDL, LDL cholesterol), triglycerides, gamma glutamyl transferase, total and direct bilirubin, alkaline phosphatase (ALP), alanine aminotransferase (ALAT), aspartate aminotransferase (ASAT), creatine phosphokinase (CPK), lactate dehydrogenase (LDH).

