2.2.2 Secondary Efficacy Endpoints

Cycles of breastfeeding women will be excluded from the efficacy analyses but included in the analyses regarding safety and tolerability.

Secondary efficacy endpoints are:

- Pearl Index based on overall cycles (overall PI) in women aged ≤ 35 years
PI based on overall cycles will include all pregnancies which will occur during the trial in women aged ≤ 35 years (at the time of trial enrollment).
- PI for method failures in women aged ≤ 35 years
Method failures PI will include all pregnancies of women who used the IMP correctly. Pregnancies are to be excluded from the calculation if in medication cycles of conception or in the previous medication cycles depending on the date of conception:
 - not all active tablets are taken (based on returned medication, recordings in the e-diary and non-compliance based on DRSP levels, if necessary)

- there is a tablet free interval between the previous medication cycle and the medication cycle of conception
- vomiting or diarrhea is documented
- administration of prohibited prior or concomitant therapy as detailed in Section 10.7 of the Clinical Trial Protocol is documented
- Pregnancy ratio in women aged ≤ 35 years (Life table analysis)

In addition to PI analysis, method failure life table analysis and life table analysis on evaluable cycles will be performed in women aged ≤ 35 years (at the time of trial enrollment) in order to have the pregnancy rate at each cycle and cumulative pregnancy rates for 6 and 13 cycles. For life table analysis on evaluable cycles, only medication cycles of non-breastfeeding women will be considered as evaluable as defined in 2.2.1 and will be included in analysis. If the cycle is not evaluable but the subject became pregnant in this cycle, the cycle has to be included in the analysis. All pregnancies following premature termination of IMP will not be included in calculations if they occur later than seven days after the last tablet intake (active or placebo). Method failure pregnancy rates similar to method failure PI will include only those cycles of women who use the IMP correctly and include only perfect medication cycles as described in Section 5.5 of non-breastfeeding women.

- Overall PI, PI for method failures, PI for evaluable cycles and pregnancy ratio (life table analysis) in all women

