Method failure pregnancy*	All on-drug pregnancies of women who used the IMP correctly. Pregnancies are to be excluded from the calculation if in medication cycles of conception or in the previous medication cycles depending on the date of conception: 
 - not all active tablets are taken (based on returned medication, recordings in the e-diary and non-compliance based on DRSP levels, if necessary) - there is an active tablet free interval between the previous medication cycle and the medication cycle of conception. Tablet free interval will be determined by record from treatment diary. - vomiting or diarrhea is documented - administration of prohibited prior or concomitant therapy as detailed in Section 10.7 of the Clinical Trial Protocol is documented
Exposure cycles	28-day cycles, where at least one treatment diary entry of IMP intake is available. In addition, a cycle will be an exposure cycle if the subject become pregnant during this cycle regardless this cycle was a 28-day cycle or not.
Evaluable cycle	Cycles are exposure cycles with intercourse without back-up contraceptive at least once per cycle based on electronic diary question 'Did you have sexual

	
intercourse since the beginning of the cycle?" and answered with: 'Yes I had sexual intercourse without additional contraception'.
 
Also, cycle is to be defined as evaluable if:
 
 - Subject became pregnant at the respective cycle regardless back-up contraception was used or not. - Cycle has missing answer about intercourse or answered "I had NO sexual intercourse at all" but subject became pregnant at the respective cycle. 
Cycle will not be defined as evaluable if subject did not become pregnant and:
 
 - The question was answered with 'Yes I had sexual intercourse with additional contraception'. - Cycles with NO intercourse. - Cycle has missing answer about intercourse.
Perfect cycle*	
Evaluable cycles which have no:
 
 - >48h tablet free interval during the second IMP intake till day 24 of each cycle or >144h interval between the last IMP intake and the first IMP intake in consecutive cycles. Tablet free interval calculation will not take into account cycle days 25-28. - 4 or more days with forgotten tablets intake during 1-24 cycle days. - Protocol deviations having effect on this cycle.

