* Method failure pregnancies will be only those which occurred during the perfect cycles, e.g., if pregnancy will contradict method failure definition then the cycle in which pregnancy occurred could not be called perfect cycle and vice versa.

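### The method-failure rule has no cut-off at recognition of the pregnancy, so tablets stopped or vomiting recorded because of the pregnancy can remove it from the method-failure Pearl Index and life tables

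*SAP*

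**What the plan says.** SAP 5.5 (definition of method failure pregnancy) counts on-drug pregnancies in women who used the product correctly. A pregnancy is "excluded from the calculation if in medication cycles of conception or in the previous medication cycles depending on the date of conception" one of four things happened. Two matter here: "not all active tablets are taken (based on returned medication, recordings in the e-diary and non-compliance based on DRSP levels, if necessary"), and "vomiting or diarrhea is documented". Section 2.2.2 states the same rule. The unit is the cycle. The conception date helps to choose which cycle is examined, and no item separates events before conception or recognition from events after.

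The perfect-cycle definition in 5.5 also runs through the active phase. It bars a tablet-free gap of more than 48 hours up to Day 24, and "4 or more days with forgotten tablets intake during 1-24 cycle days". The footnote ties the two definitions together: "Method failure pregnancies will be only those which occurred during the perfect cycles", and a pregnancy that fails one definition fails the other.

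The plan expects shortened conception cycles, because "a cycle will be an exposure cycle if the subject become pregnant during this cycle regardless this cycle was a 28-day cycle or not". The flow chart in SAP section 1 puts a urine pregnancy test at Visits 2 to 5, "Day 20 ± 2 of medication cycle" (cycles 1, 3, 6 and 9). SAP 2.5 gives 24 active tablets per cycle. SAP 5.1.1 lists pregnancy as a withdrawal reason.

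**The concern.** The method-failure index is meant to describe pregnancy under correct use. A tablet left untaken because the woman already knows she is pregnant, or vomiting caused by the pregnancy, cannot have contributed to the conception. Excluding on such an event lets the outcome decide whether the outcome is counted. A non-pregnant woman cannot lose a cycle this way, so the effect runs in one direction.

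The evidence sources make this a practical matter. Returned medication is the first source named for missed tablets, and note 18 to the flow chart has drug accountability performed when a subject is discontinued prematurely. A woman withdrawn for pregnancy in mid-cycle would hand back unused active tablets, and under the rule these count against her. Method-failure pregnancies are likely to be few, so each one lost moves the index noticeably.

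**Working it through.** **1. The plan's own figure.** The documents give no planned method-failure count, perfect-cycle count or method-failure index. The only planning figure is 920 subjects for 5000 evaluable cycles (SAP 2.6): 920 × 13 × (1 − 0.248) × (1 − 0.45) = 4947 cycles, 1.1% below 5000. It reproduces, but it sets only the scale.

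**2. What the rule does to a correct user who stops after Day d of her conception cycle.** Active tablets not taken = 24 − d.

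| Last tablet | Active tablets not taken | All-active-tablets clause | Four-day criterion |
|---|---|---|---|
| Day 18 | 6 | disqualified | disqualified |
| Day 20 | 4 | disqualified | disqualified |
| Day 21 | 3 | disqualified | not triggered |
| Day 22 | 2 | disqualified | not triggered |

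The all-active-tablets clause is enough on its own, and through the footnote the cycle leaves with the pregnancy.

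**3. Who is exposed.** Let L be the days from conception to detection and stopping. A pregnancy is lost through stopped tablets only if conception day + L ≤ 23. That means conception by Day 13 (L = 10), Day 9 (L = 14) or Day 2 (L = 21). With conception assumed uniform over 28 days and testing possible on any day, the upper limits are 13/28 = 46%, 9/28 = 32% and 2/28 = 7%.

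**4. Scheduled clinic tests only.** Share = (20 − L)/28 × w, where w is the share of exposure in cycles 1, 3, 6 and 9. Three values of w:
- Equal weights: 4/13 = 0.308.
- 45% dropout spread evenly, retention at mid-cycle k = 1 − 0.45(k − 0.5)/13: (0.983 + 0.913 + 0.810 + 0.706)/10.075 = 0.339.
- The same, leaving out cycle 1: 2.429/10.075 = 0.241. Naive and previous users start on the first or second day of bleeding (SAP 2.3), so uniform early conception is least credible in that cycle.

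| L | (20 − L)/28 | w = 0.308 | w = 0.339 | w = 0.241 |
|---|---|---|---|---|
| 10 days | 0.357 | 11.0% | 12.1% | 8.6% |
| 14 days | 0.214 | 6.6% | 7.3% | 5.2% |
| 21 days | 0 | 0% | 0% | 0% |

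Moving the visit within Day 18–22 at equal weights gives 8.8–13.2% (L = 10), 4.4–8.8% (L = 14) and 0–1.1% (L = 21).

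**5. Effect on the index.** Index = 1300 × pregnancies / cycles. Assume 10 otherwise qualifying pregnancies in 4000 perfect cycles; each removal takes one pregnancy and one cycle. The limits are exact Poisson, with the upper limit from the 0.975 quantile on 2(x + 1) degrees of freedom, not the upper-limit formula as printed in SAP 5.5.

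| Removed | Index | 95% CI |
|---|---|---|
| 0 | 3.25 | 1.56–5.98 |
| 1 | 2.93 | 1.34–5.55 |
| 4 | 1.95 | 0.72–4.25 |

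Removing k of m pregnancies lowers the index by about k/m. At 5–12% of 10, the expected loss through scheduled visits is 0.5 to 1.2 pregnancies.

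**The case against.** *The wording is loose, and the data review meeting can put it right.* The definition opens with correct use, refers to the date of conception, and SAP 3.3 has a team including a physician assign each pregnancy to its category and cycle. This stands to the extent that removal is not certain in every case. A reader might infer that a conception cycle cut short before Day 24 can never be a method failure; the meeting's discretion means the documents do not go that far. But no written rule tells the meeting to disregard later events, and its vomiting and diarrhea listing (DRM02) is organised by cycle. The meeting report is not among the documents, and of the protocol only the synopsis is available, so a rule recorded elsewhere cannot be ruled out.

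*The group exposed is narrow.* This stands. It is tempting to say that pregnancies found early in a cycle drop out. The routine home test is done at the start of each new cycle (flow chart, note 8), so such pregnancies were normally conceived in the cycle before, and stopping then falls outside the window. With L of 14 days or more, none found by Day 14 was conceived in that cycle; with L = 10, 4/28 of conceptions could be.

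*The perfect-cycle item speaks of forgotten tablets, serum confirmation is still needed after a positive urine test, and no text seen says tablets stop the same day.* This weakens the four-day criterion, which in any case applies only if stopping is after Day 20 or earlier. It does not touch the clause on taking all active tablets.

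*The percentages are assumption.* This stands. The lag, uniform conception and immediate stopping are not in the documents. In addition, the method-failure tables count confirmed pregnancies, and 5.5 defines these as starting from a positive home test. Read literally, a pregnancy found only at a clinic visit may not enter those tables at all. Pregnancy-related vomiting within the conception cycle cannot be quantified from the documents. Chance missed tablets after conception also disqualify, but that is not an effect of the pregnancy.

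*Exclusions are already reported.* Table 15.1.7.1.1 will show deviations that remove pregnancies from the method-failure analysis. That helps, but its description asks for no timing relative to conception or recognition.

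*Cutting off every criterion at conception would create the opposite bias.* This stands. Non-pregnant cycles must be perfect through Day 24. Forgiving chance misses in conception cycles alone would push the index up, and conception dates can rest on urine hCG or the investigator's estimate (SAP 2.2.1).

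**Conclusion.** The concern holds in this limited form: the written rule lets consequences of a recognised pregnancy disqualify it as a method failure, and neither the reference to the conception date nor the data review meeting sets a cut-off that prevents it. The women affected conceived early and were recognised as pregnant before Day 24 of the same cycle. Where the disqualifying event results from the pregnancy, the bias can only be downward.

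The size is unknown. Roughly 5–12% of otherwise qualifying pregnancies through scheduled Day 20 tests rests on uniform conception, a 10–14 day lag and prompt stopping; at a 21-day lag the figure is 0%. Any one of these figures taken alone would claim more than the documents support.

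Only the secondary method-failure Pearl Index and life tables are affected. A reader might infer that the main efficacy result is biased too. It is not: the primary index on evaluable cycles and the overall index do not apply these exclusions. The rule should be corrected, but the trial's primary conclusion does not depend on it.

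**What to change.** In SAP 2.2.2 and 5.5 (method failure pregnancy, perfect cycle and the footnote), add this rule: for a conception cycle, active tablets not taken, and vomiting or diarrhea recorded, after the first positive pregnancy test, or after treatment was stopped because of pregnancy, do not disqualify the pregnancy or its cycle. All earlier events count exactly as they do for non-pregnant cycles. This concerns classification only and says nothing about when tablets should be stopped.

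Add one sensitivity analysis of the method-failure index that counts events only up to the estimated conception date plus a stated allowance for dating error. Note beside it that it treats conception cycles more leniently than non-pregnant ones. It also covers pregnancy-related vomiting before the first positive test, which the main rule would still count.

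The cost is a sentence in each section, a date comparison in the programming and one extra table. The estimated conception date, last intake date and termination reason are already collected; confirm that the date of the first positive home test is recorded too. The method-failure index may come out slightly less favourable.
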